### **Preparation of Donor Stool**

Donors will be advised to collect and submit fresh stool sample on the day of FMT after arriving at the hospital in sterile plastic collection containers. All stool samples will be obtained 6 hours before the procedure. Stool specimen (preferably Bristol Stool Type 4 or 5) with a weight of ~30 g (about ~ 2 cm^3) will be considered adequate. 100 mL of sterile normal saline will be added to the stool sample and homogenized with a blender (Morphy Richards ® HBCP Hand Blender @<https://www.amazon.in/Morphy-Richards-HBCP-400-Watt-Blender/dp/B0073QIN6C>) for 2-4 minutes in pulses of 30 seconds with 10 seconds wait in between each pulse. The homogenous suspension will be then filtered through sterile

gauze pieces, 3-4 times until the filtrate was devoid of roughage. Personnel involved in stool specimen preparation will be required to wear eye shield, masks and fluid resistant gowns.

### **The FMT Procedure**

In the Fecal Microbiota Transplantation procedure 100 ml volume of strained and filtered stool will be delivered through a nasojejunal tube. The recipient patient will be kept nil per oral for at least 4 hours prior to the stool instillation. 100 mL of freshly prepared stool suspension will be given. IV antibiotics will be continued as per treating physician's decision in the event of active sepsis based on culture and sensitivity. The duodenal tube will be flushed with normal saline (30mL) after the stool instillation. The patient will be allowed to consume liquid diet two hours after the procedure. All patients will continue on salt restriction, diuretics, and 1.5g/kg per day of plant and egg based protein and weight based recommended calorie intake as prescribed by the dietician. Intravenous albumin will be continued as indicated during hospitalized period. While rifaximin and other non-absorbable antibiotics will be withheld, disaccharides will be permitted to have 2-3 soft stools per day.

### **Follow Up post FMT**

Follow up of patients will be done at 7, 30, 90 and 180 days post FMT. During follow up patients will be evaluated for clinical parameters, routine biochemical monitoring and inflammatory markers for determining status of disease status.

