**Objectives:**

**Primary Objective:** To assess the difference in 180-day mortality between the FMT group and the SOC group.

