#### **4. METHODOLOGY**

**Study design:** This will be an institute based prospective pilot study carried out in Postgraduate Institute of Medical Education and Research, Chandigarh from July 2018 to June 2020.

**Study period:** 15 months (from August 2018 to November 2019)

**Recruitment Period:** 10 months (August 2018 to May 2019)

**Sample Size:** 20 consecutive patients satisfying the selection criteria in each arm

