### **Pre FMT**

Participants randomized to the FMT arm will be given pretreatment antibiotics to decrease the host bacterial load, lower diversity, and enable a colonic colonization of the donor microbiota. Lactulose and rifaximin will be continued for all patients as per indication. A 5-day broad-spectrum coverage regimen will be used (metronidazole 500 mg orally three times daily, ciprofloxacin 500 mg orally twice-daily, and amoxicillin 500 mg orally three times daily) prior to administration of FMT. All antibiotics will be discontinued at least 12 hours before FMT to ensure that these agents would not impact the instilled microbiota. Participants in the SOC arm will not receive antibiotic pretreatment or FMT, but follow-up will be identical on days 7, 30 and 90 post FMT post randomization.

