### **Donor Selection Criteria:**

Family members will be interviewed and screened for eligibility for being a FMT donor since pooled stool donor facility is not available at our institute. The subjects will be screened for routine laboratory tests, hemogram, fasting blood sugar, liver function tests, lipid profile, stool routine and microscopy for cysts, parasites, ova stool for occult blood, stool cultures, HBsAg, anti HCV, HIV 1 and 2, Clostridium difficile and VDRL. A written informed consent will be taken from the donor to donate fresh stool sample on day of FMT. Donors will be excluded if they had abnormal bowel motions, abdominal complaints, extensive travel history or predisposing factors for potentially transmittable diseases, occasional or chronic alcohol intake, and history of substance abuse or fail to provide consent. Subjects will also excluded if they are less than 18 or more than 60 years of age, had primary or secondary immunosuppressed state, had enteric infections within last 2 months, history of inflammatory bowel disease, prior abdominal surgery, pancreatic disease, gastrointestinal neoplasms in the past, metabolic syndrome, systemic autoimmunity, atopic diseases or on treatment for the same, food and respiratory allergies, chronic neurologic disorders, neuro-developmental disorders, have had antibiotics within the last 2 months. Donors will be advised to eat food based on recommended daily allowance as calculated by dietician and not permitted to eat street foods or attend public functions or eat at family functions or parties. They will not be allowed social consumption of alcohol or tobacco during a period of one week.

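### The 180-day mortality comparison has no stated day 0, its only day-180 schedule is counted from FMT, and nothing says deaths before FMT or patients who never receive it are counted as randomised

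*Combined protocol and SAP*

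**What the plan says.** The combined protocol and SAP states the primary objective as "To assess the difference in 180-day mortality between the FMT group and the SOC group" (Objectives). It gives no time origin.

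The only schedule that reaches day 180 is in Follow Up post FMT: "Follow up of patients will be done at 7, 30, 90 and 180 days post FMT". Under Pre FMT, the control arm is described twice: "Participants in the SOC arm will not receive antibiotic pretreatment or FMT", and "follow-up will be identical on days 7, 30 and 90 post FMT post randomization". The second phrase joins two origins. The Statistical Analysis section uses a third wording, days of the study.

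Pre FMT also fixes the order of events. Patients are randomised first; those in the FMT arm then take antibiotics ("A 5-day broad-spectrum coverage regimen will be used"), and "All antibiotics will be discontinued at least 12 hours before FMT". No longest interval from randomisation to FMT is given.

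Donors are screened family members, "since pooled stool donor facility is not available at our institute" (Donor Selection Criteria). Having an eligible donor is not among the inclusion criteria, and the text does not say whether donors are screened before or after randomisation. Annexure 1 lets patients leave the study at any point.

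The sample size is "20 consecutive patients satisfying the selection criteria in each arm". The Statistical Analysis section names no analysis set and no censoring rule. It does not say how to treat deaths or withdrawals before FMT.

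**The concern.** A randomised comparison is protected only if follow-up starts at the same point in both arms and everyone randomised is counted. Here the antibiotic course is part of the assigned strategy and is given in one arm only. If events during it are left out, or patients who do not reach FMT are dropped, the FMT arm becomes a group selected by surviving and completing pretreatment. The SOC arm has no matching selection.

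The gap also affects data collection. A patient randomised to FMT who never receives it has no date from which the written visits can run, so day-180 status might not be collected on any defined schedule.

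The title calls the trial open-label. A counting rule left open can therefore be settled after outcomes are known by arm, and with 20 patients per arm each patient is 5 percentage points of that arm's mortality.

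**Working it through.** **Plan's own figure.** The plan gives 20 per arm without event rates, effect size or power, so there is no calculation to reproduce. All mortality rates below are assumptions, as is any gap above 5.5 days.

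**1. Time origins side by side**

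| Section | Origin as written | Reaches day 180? |
|---|---|---|
| Objectives (primary) | none | yes |
| Follow Up post FMT | FMT | yes |
| Pre FMT (SOC follow-up) | FMT and randomisation in one phrase | no |
| Assessment of Pro-inflammatory Cytokines | baseline, then day 28 after FMT | not applicable |
| Statistical Analysis | the study | no |

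The day 180 missing from two of these rows is a separate defect and carries no weight here.

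**2. Minimum gap from randomisation to FMT.** 5 days of antibiotics + 0.5 day off them = about 5.5 days.

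**3. Offset bias in the FMT arm.** Let m be 180-day mortality, g the gap in days, and S(t) = exp{ln(1−m) × (t/180)^k}, with k = 1 for constant hazard. Bias is the result minus m.

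- A, all deaths counted to FMT+180: 1 − S(180+g)
- B, clock from randomisation, pre-FMT deaths dropped: 1 − S(180)/S(g)
- C, clock from FMT, pre-FMT deaths dropped: 1 − S(180+g)/S(g)

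Example, m = 0.20, g = 5.5, k = 1: S(5.5) = 0.9932 and S(185.5) = 0.7946. A = 0.2054, or +0.54 points. B = 1 − 0.80/0.9932 = 0.1945, or −0.55 points.

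| Points, m = 0.20 / 0.30, k = 1 | A | B | C |
|---|---|---|---|
| g = 5.5 | +0.54 / +0.76 | −0.55 / −0.77 | 0 / 0 |
| g = 14 (assumed) | +1.38 / +1.92 | −1.40 / −1.97 | 0 / 0 |

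The hazard shape matters somewhat. At g = 5.5 with an assumed falling hazard (k = 0.75), B is −1.32 / −1.85 and C is −0.90 / −1.27. With an assumed rising hazard (k = 1.5), A is +0.82 / +1.14 and B is −0.10 / −0.13.

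For scale, the standard error of the difference is √(2m(1−m)/20) = 12.6 points at m = 0.20 and 14.5 at m = 0.30.

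**4. Chance of at least one pre-FMT death among 20.** P = 1 − S(g)^20.

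- k = 1, g = 5.5: 1 − 0.9932^20 = 12.7% at m = 0.20, and 19.6% at m = 0.30
- k = 1, g = 14: 29.3% and 42.6%
- k = 1.5, g = 5.5: 2.4% and 3.7%
- k = 0.75, g = 5.5: 27.8% and 40.6%

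**5. Chance that dropping one such death changes the test result.** Let x and y be deaths among 20 in the FMT and SOC arms, binomial with the assumed rates. Given x, the chance that at least one death preceded FMT is 1 − (1−q)^x, where q = (1 − S(g))/m. Sum the product of these probabilities over all tables where two-sided Fisher's P lies on different sides of 0.05 for x/20 and (x−1)/19, each against y/20.

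| FMT vs SOC mortality (k = 1) | g = 5.5 | g = 14 |
|---|---|---|
| 20% vs 20% | 0.15% | 0.4% |
| 30% vs 30% | 0.22% | 0.5% |
| 20% vs 30% | 0.6% | 1.4% |
| 20% vs 50% | 2.0% | 4.6% |

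Tables that cross do exist: 4/20 vs 10/20 gives P = 0.096, and 3/19 vs 10/20 gives 0.041. That needs SOC mortality of 50%. At 4/20 vs 6/20, P goes from 0.72 to 0.45 (3/19 vs 6/20), and nothing crosses.

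**6. Patients who never reach FMT.** Dropping two survivors moves the FMT-arm rate the other way: 4/20 = 20.0% becomes 4/18 = 22.2%, and 6/20 = 30.0% becomes 6/18 = 33.3%.

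**The case against.** The strongest reply is that Follow Up post FMT is a visit schedule and does not define the endpoint. Mortality is given no origin at all, SOC follow-up is called identical, and the analysis section's days of the study can be read as one common clock. A reader might infer that the protocol prescribes FMT as day 0 for deaths in one arm and randomisation in the other. The documents do not go that far. Two clocks are the natural result of following the only day-180 schedule, and a matched SOC date would be possible, though none is described.

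Comparison as randomised can likewise be read into the wording of the objective and the randomisation section, which speak of the two groups. That is a reasonable guess at intent, but it does not say what happens to a patient with no FMT date.

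The donor argument rests on silence. The text does not place donor screening after randomisation; it simply does not place it. Non-receipt is foreseeable, but its frequency is unknown.

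Early risk may also be low. Entry is limited to MELD 12-21. Ongoing infection needing antibiotics is excluded, as are spontaneous bacterial peritonitis, gastrointestinal bleeding or overt encephalopathy in the last 14 days. This supports the lower figures in step 4, but the documents cannot settle the hazard shape.

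Finally, one patient can shift P in any trial of 20 per arm. That is fair, and single tables that cross 0.05 should not be read as the likely outcome.

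**Conclusion.** The concern holds as a gap in the definition of the primary comparison. Day 0 is not stated, the only day-180 follow-up is counted from an event that one arm does not have, a patient who never receives FMT has no anchor, and no rule counts pre-FMT deaths or such patients as randomised.

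Two further inferences are not supported. One is that the clock offset materially distorts the result. At the minimum gap it is worth under 1 point in either direction with constant hazard, and at most about 1.9 points under the other hazard shapes tried, against a standard error of 12.6-14.5 points. The other is that the omission necessarily favours FMT, or is likely to change significance. The sign depends on which patients and events are left out, and dropping one pre-FMT death crosses 0.05 with probability about 0.1-0.6% at 5.5 days and 0.4-1.4% at an assumed 14 days.

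These sizes rest on assumed 180-day mortality of 20-30%; the crossing probabilities also assume constant hazard. The weight of the point is the need to keep the comparison as randomised in an open-label trial. The change should be made, but the omission does not by itself undermine the trial.

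**What to change.** - Set day 0 as the date of randomisation in both arms for mortality, complications and adverse events, and count events from that date, including the antibiotic period.
- Analyse every randomised patient in the assigned arm whether or not FMT was given. Present an analysis restricted to patients who received FMT as sensitivity only.
- Follow patients who never receive FMT to day 180 from randomisation, and time their score and cytokine visits from randomisation too.
- If score and cytokine visits in the FMT arm stay timed from FMT, state the matching SOC anchor and report actual days from randomisation.
- Reconcile the time origin across Objectives, Pre FMT, Follow Up post FMT, Assessment of Pro-inflammatory Cytokines and Statistical Analysis.

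The cost is small. Because FMT comes after randomisation, follow-up to 180 days after FMT already covers 180 days after randomisation. With dates of death recorded, only patients who never reach FMT need a new anchor. The downsides are slight dilution of the effect by patients who never receive FMT and a little more event recording. No treatment changes.

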### **Clinical and Laboratory Assessment**

All patients will undergo a detailed clinical evaluation including history and physical examination, and routine biochemical and imaging evaluation. Investigations for etiology of cirrhosis will be performed as required on a case by case basis. Patients will be worked up for chronic liver disease with proper history, clinical examination and investigations which will include viral markers (HbsAg, Anti-HCV, Total anti-Hbc, AIH markers (ANA/SMA/LKM), serum ceruloplasmin, iron profile, celiac work up, NAFLD work up and radiological investigations for cirrhosis and as otherwise indicate

### **Management post FMT**

All patients (experimental arm as well standard of care arm) will be managed by standard medical management in the department of Hepatology, PGIMER. Antibiotics will be given as per protocol and subsequently upgraded according to culture and sensitivity reports. Acute kidney injury will be managed with intravenous 20% human albumin with vasoactive agents if needed and dialysis when indicated. Patients with hepatic encephalopathy will be treated with lactulose and rifaximin. Diuretics will be given for ascites if not precluded by renal failure or hepatic encephalopathy. Inotropes will be given for hypotension and endotracheal intubation with mechanical ventilation will be done for respiratory failure as well as for airway protection for advanced HE.

### **Assessment of Pro-inflammatory Cytokines**

Cytokines (,interleukin [IL]1b, and IL6 will be measured in plasma derived from cirrhoticpatients using specific enzyme-linked immunosorbent assaykits (RayBiotech, Inc, Norcross, GA) according to the manufacturer's protocol. The plate will be read at 450 nm. Absorbance will be converted to picograms per milliliter using a standardcurve prepared with recombinant human IL1b, IL6. Measures will be taken at base line and 28 days post FMT.

## **4. STATISTICAL ANALYSIS**

The results will be expressed as mean  $\pm$  standard deviation (SD) or median with range. Comparisons between groups will be performed using student's t-test or the Mann–Whitney U test. For categorical data chi-square test or Fisher's exact test will be applied. A value of  $P < 0.05$  will be taken as significant. The results will be analyzed at baseline and at day 7, 30 and 90 of the study. The in hospital survival curves will be made by the Kaplan-Meier method and compared with the log-rank test. All statistical tests will be done by Microsoft Excel and SSPSS Software version 18.

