**Secondary Objective**

1. To assess and compare the changes in liver function in both groups based upon
  - CTP score at 28 days, 90 days and 180 days
  - MELD Score at 28 days, 90 days and 180 days
  - MELD Na Score at 28 days, 90 days and 180 days
2. To compare the complications in both groups in a follow-up period of 180 days
3. Changes in inflammatory markers (IL-1b, IL-6) in both groups at 28 days

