### **Inclusion Criteria**

1. 18-75 years
2. Confirmed advanced cirrhosis of any aetiology with a MELD score between 12 and 21.  
The diagnosis of liver cirrhosis will be based on clinical, radiological, or histological criteria
3. Patients must be deemed to have capacity to consent to study.

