### **Randomization of patients**

Patients with decompensated cirrhosis who will be enrolled in the study after satisfying the selection criteria will be randomized into two groups 1:1 ratio using a random number generator

**Group 1(Experimental Arm):** Patients with decompensated cirrhosis who will receive Fecal MicrobiotaTransplantation via nasojejunal tube as well as traditional treatment for decompensated cirrhosis.

**Group 1(Standard of Care Arm):** Patients with decompensated cirrhosis who will receive standard medical treatment for decompensated cirrhosis.

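### Changes in liver scores and cytokines are secondary objectives, but the planned group comparisons neither define the analysed variable nor adjust for baseline

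*Combined protocol and SAP*

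**What the plan says.** In the combined protocol and SAP, the first item under Secondary Objective is "To assess and compare the changes in liver function in both groups based upon" CTP, MELD and MELD-Na. Each score has the same three time points, for example "MELD Score at 28 days, 90 days and 180 days". The third item is "Changes in inflammatory markers (IL-1b, IL-6) in both groups at 28 days". The primary objective is separate: "To assess the difference in 180-day mortality between the FMT group and the SOC group".

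For continuous outcomes, the section 4. STATISTICAL ANALYSIS says "Comparisons between groups will be performed using student's t-test or the Mann–Whitney U test". It names no analysed variable, covariate or model. Baseline appears there only as one of the days on which results are analysed.

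Baseline values should largely exist. MELD is an entry criterion ("Confirmed advanced cirrhosis of any aetiology with a MELD score between 12 and 21"), and Assessment of Pro-inflammatory Cytokines schedules a baseline and a day 28 measurement. For CTP and MELD-Na, a baseline value is implied by the baseline analysis but not stated outright.

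The sample is "20 consecutive patients satisfying the selection criteria in each arm", described under Study design as a pilot. Patients are "randomized into two groups 1:1 ratio using a random number generator", and no stratification is stated.

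**The concern.** An objective worded as change suggests change from baseline, but the analysis section does not carry this into a definition. A t-test on the day-90 score and a t-test on the change to day 90 both fit the text, and they can give different answers from the same data.

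Neither handles a chance baseline difference well. A follow-up comparison ignores it. A change-score comparison subtracts it in full, which over-corrects whenever the regression slope of follow-up on baseline is below 1. With 20 per arm such differences are common and precision is scarce. At stake are the continuous secondary outcomes, to which the plan applies P < 0.05.

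**Working it through.** The plan gives no power, SD, correlation or effect size, so there is no figure of its own to reproduce.

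**Inputs from the documents.** n = 20 per arm (4. METHODOLOGY); entry MELD 12 to 21 (Inclusion Criteria); P < 0.05 (4. STATISTICAL ANALYSIS; two-sided assumed).

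**Assumptions.** Baseline-to-follow-up correlation r = 0.2 to 0.7; k = follow-up SD / baseline SD = 1, 1.25 or 1.5; bivariate normal, complete data.

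**Variance.** Estimating one slope costs a factor 1 + 1/(2n − 4) = 1 + 1/36 = 1.028.

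- ANCOVA / follow-up t-test = (1 − r²) × 1.028, for any k. At r = 0.5: 0.75 × 1.028 = 0.77.
- ANCOVA / change t-test = k²(1 − r²) × 1.028 / (k² + 1 − 2rk). At r = 0.5, k = 1.5: 2.25 × 0.75 × 1.028 / 1.75 = 0.99.

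| r | v follow-up | v change, k = 1 | v change, k = 1.25 | v change, k = 1.5 |
|---|---|---|---|---|
| 0.2 | 0.99 | 0.62 | 0.75 | 0.84 |
| 0.3 | 0.94 | 0.67 | 0.81 | 0.90 |
| 0.5 | 0.77 | 0.77 | 0.92 | 0.99 |
| 0.7 | 0.52 | 0.87 | 1.01 | 1.03 |

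Against the follow-up t-test, ANCOVA loses only below r = √(1 − 1/1.028) = 0.16, and by at most 2.8%. With 15 evaluable per arm the factor is 1 + 1/26 = 1.038, and each ratio rises by about 0.01.

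**Power** for an assumed effect of 0.8 follow-up SD (noncentral t for the t-tests, simulation for ANCOVA), as follow-up / change / ANCOVA:

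| r | k = 1 | k = 1.5 |
|---|---|---|
| 0.2 | 69 / 50 / 70% | 69 / 62 / 70% |
| 0.3 | 69 / 55 / 72% | 69 / 68 / 72% |
| 0.5 | 69 / 69 / 80% | 69 / 80 / 80% |
| 0.7 | 69 / 89 / 93% | 69 / 93 / 93% |

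With no true effect, each of the three analyses rejects in about 5% of simulated trials. With the 0.8 SD effect, the follow-up and change t-tests fall on opposite sides of P = 0.05 in about 29–32% of trials at k = 1 and 19–25% at k = 1.5.

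**Chance imbalance.** If baseline MELD is uniform on 12–21, its SD is 9/√12 = 2.6, and the SE of the arm difference is 2.6 × √(2/20) = 0.82. A difference of at least 1 point then has probability 22% (11% if the SD is 2.0). One point of imbalance shifts the follow-up comparison by rk and the change comparison by rk − 1:

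| r | follow-up, k = 1 | change, k = 1 | follow-up, k = 1.5 | change, k = 1.5 |
|---|---|---|---|---|
| 0.3 | 0.30 | −0.70 | 0.45 | −0.55 |
| 0.5 | 0.50 | −0.50 | 0.75 | −0.25 |
| 0.7 | 0.70 | −0.30 | 1.05 | +0.05 |

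**Effect of the MELD entry limits.** Baseline MELD is truncated and follow-up MELD is not, which lowers r and raises k. As an illustration, take equal SDs before restriction, r = 0.5 or 0.7, and a baseline SD halved by eligibility. The residual variance is 1 − r², and the change-score variance is (1 − r²) + (1 − r)² × 0.25. ANCOVA / change is 0.75 × 1.028 / 0.8125 = 0.95 at r = 0.5, and 0.51 × 1.028 / 0.5325 = 0.98 at r = 0.7. For MELD the k = 1 column is therefore the optimistic one.

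The Mann-Whitney test was not evaluated.

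**The case against.** The strongest reply is that this is a preference, not an error. The trial is a pilot, the outcomes are secondary, and the planned t-tests hold their error rate. If change from baseline is the intended variable, the comparison with a follow-up t-test is beside the point, and for MELD the remaining gain may be negligible. Mann-Whitney is half of the quoted sentence and the likely choice for skewed cytokines, yet no gain over it has been computed. All of this stands. It limits the size of the point but does not supply the missing definition.

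Deaths are a second reply. Later scores exist only for survivors, a group formed after randomisation, and baseline adjustment does not cure that. This also stands, and it applies equally to the planned tests.

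A reader might infer that the plan's tests are invalid or that the false-positive rate is inflated. If whichever of the two t-tests looked better were reported, the error rate per endpoint would be roughly 8% to 9.5% under the same assumptions. But nothing in the documents says results will be chosen in that way. The opposite inference, that randomisation fully protects these comparisons at every visit, also fails once patients have died.

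**Conclusion.** The omission is certain: the analysed variable is not defined and baseline is not used. Its cost is uncertain, because every correlation, SD ratio and effect size above is assumed. In the range examined, ANCOVA is never more than about 3% worse in variance than the better t-test. It is often clearly better than a follow-up t-test, and anywhere from clearly better to no better than a change-score t-test. For MELD the lower end is the more plausible.

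The mortality primary is unaffected. The documents do not support reading this as correction of an invalid analysis, or as a demonstrated advantage over Mann-Whitney. It is a cheap improvement to secondary analyses.

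**What to change.** In 4. STATISTICAL ANALYSIS:

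- State that CTP, MELD and MELD-Na, at each analysis day named in the objectives, are compared by ANCOVA of the follow-up value on arm and baseline value. Do the same for log IL-1b and log IL-6 at day 28 only, since no other follow-up cytokine measurement is scheduled.
- Define baseline as the value taken before randomisation, and so before the antibiotic pretreatment that Pre FMT gives to one arm only.
- Report the adjusted difference with its 95% CI, back-transformed to a ratio for cytokines.
- Keep the t-test and Mann-Whitney as sensitivity analyses, and say which variable they use. If log cytokines are clearly non-normal or often below the detection limit, use a rank-based baseline-adjusted analysis.
- Report deaths by arm beside each comparison, and state that it is restricted to survivors.

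The cost is a short paragraph, one degree of freedom (at most about 3% in variance), a linearity assumption, and a rule for values below the detection limit. No extra visits or assays are needed, provided that the baseline values precede randomisation; the documents do not state this timing.

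A separate point, which adds no weight here: the analysis days (7, 30, 90), the objectives (28, 90, 180) and the visits in Follow Up post FMT (7, 30, 90, 180) must be reconciled so that day 180 is analysed.

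### The cytokine analysis has no stated scale and no baseline adjustment: if IL-1b and IL-6 are right-skewed and absolute change is tested, power is lost that one log-scale ANCOVA would recover

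*Combined protocol and SAP*

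**What the plan says.** - **Objective.** The third item under Secondary Objective is "Changes in inflammatory markers (IL-1b, IL-6) in both groups at 28 days". It does not say whether change means an absolute difference, a percentage or a ratio.
- **Measurement.** Assessment of Pro-inflammatory Cytokines says "Absorbance will be converted to picograms per milliliter using a standardcurve prepared with recombinant human IL1b, IL6", and "Measures will be taken at base line and 28 days post FMT". Picograms per millilitre is the only unit given. No assay limit is stated, and no rule for values below one.
- **Analysis.** Section 4, Statistical Analysis, says "Comparisons between groups will be performed using student's t-test or the Mann"–Whitney U test. Summaries are mean with SD "or median with range". It names no transformation, no covariate and no criterion for choosing between the tests. Significance is P below 0.05, with sidedness not stated.
- **Size.** Section 4, Methodology, plans "20 consecutive patients satisfying the selection criteria in each arm". No power, effect size or SD accompanies that number for any endpoint.

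**The concern.** Plasma cytokine concentrations may be right-skewed, and a treatment may act on them proportionally. If so, the absolute change depends on the starting level: the same halving takes 5 off a value of 10 and 50 off a value of 100. A t-test on the raw change is then dominated by the few patients with high baselines. Mann-Whitney on the raw change is only partly protected, because the ranks are taken after the subtraction and so carry the baseline spread with them. Taking logs before comparing removes that dependence.

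Cytokine reduction appears in the research question and the study hypothesis as well as in the secondary objectives, and each patient has only one post-baseline measurement. At stake is whether the trial could detect a real reduction of moderate size in 40 patients.

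**Working it through.** **Inputs from the protocol.** 20 per arm; allocation "randomized into two groups 1:1 ratio using a random number generator"; baseline and day-28 values; significance level 0.05, taken here as two-sided.

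**Inputs assumed, because the protocol gives none.** Log-normal values; log-SD σ from 0.5 to 1.2; baseline-to-day-28 log-scale correlation ρ of 0.3, 0.5 and 0.7; FMT/SOC ratio of day-28 geometric means 0.5; no dropout.

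**The plan's own figure.** The 20 per arm cannot be reproduced, as no effect, SD or power goes with it. For reference, 20 per arm gives 80% power for a two-group comparison at a standardised difference of about 0.89.

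**Closed form for the log-scale analyses.** The effect is |ln 0.5| = 0.693.

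- ANCOVA of log day-28 on arm and log baseline: residual SD = σ√(1−ρ²).
- t-test on unadjusted log change: SD = σ√(2(1−ρ)).
- In each case d = 0.693/SD and noncentrality = d√(20/2) = 3.162d.

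At σ = 1.0:

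| ρ | ANCOVA SD, d, noncentrality | Power | Log-change SD, d, noncentrality | Power |
|---|---|---|---|---|
| 0.3 | 0.954, 0.727, 2.30 | 61% | 1.183, 0.586, 1.85 | 44% |
| 0.5 | 0.866, 0.800, 2.53 | 69% | 1.000, 0.693, 2.19 | 57% |
| 0.7 | 0.714, 0.971, 3.07 | 85% | 0.775, 0.895, 2.83 | 79% |

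Simulated ANCOVA power is 60%, 68% and 84%. It is about a point lower because the closed form ignores chance baseline imbalance. When ρ is below 0.5, √(2(1−ρ)) exceeds 1, so an unadjusted log change is noisier than the day-28 log value alone.

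**Simulation, including the raw-scale tests** (8,000 trials per setting; standard error at most √(0.25/8000) = 0.6 points). Ranges run over ρ from 0.3 to 0.7; power in %:

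| σ | t, raw change | Mann-Whitney, raw change | Mann-Whitney, day-28 value | t, log change | Log ANCOVA |
|---|---|---|---|---|---|
| 0.5 | 77–97 | 80–98 | 99 | 95–100 | 99–100 |
| 0.8 | 35–59 | 42–74 | 73–74 | 62–93 | 79–96 |
| 1.0 | 22–37 | 30–55 | 54–55 | 44–79 | 60–84 |
| 1.2 | 14–23 | 23–41 | 41–42 | 33–64 | 46–69 |

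Mann-Whitney on day-28 values is the same on the raw or the log scale and does not depend on ρ.

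**Loss against log ANCOVA at the same ρ (0.3, 0.5, 0.7), in points.**

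- σ = 1.0, t on raw change: 60.4−22.1 = 38.3; 68.3−25.9 = 42.4; 84.4−36.7 = 47.7.
- σ = 1.0, Mann-Whitney on raw change: 60.4−30.3 = 30.1; 68.3−38.2 = 30.1; 84.4−54.8 = 29.6.
- σ = 1.0, Mann-Whitney on day-28 values: 60.4−54.6 = 5.8; 68.3−55.1 = 13.2; 84.4−54.2 = 30.2.
- σ = 0.5, t on raw change: 99.2−77.2 = 22.0; 99.8−87.0 = 12.8; 100−96.6 = 3.4.
- σ = 0.5, Mann-Whitney on raw change: 99.2−80.1 = 19.1; 99.8−90.1 = 9.7; 100−98.4 = 1.6.
- σ = 0.5, Mann-Whitney on day-28 values: 99.2−98.5 = 0.7; 99.8−98.6 = 1.2; 100−98.8 = 1.2.

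**Type I error** (20,000 null trials per setting, 20 per arm). Log ANCOVA 4.7–5.1%; t on raw change 3.3–5.0%; Mann-Whitney on raw change 4.7–5.3%. Reporting the smaller of the two raw-change P values gives 6.0–6.7%. Choosing the test by a Shapiro-Wilk check gives 4.2–5.7%, which is nominal within simulation error.

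**The case against.** **The protocol does not commit to the weak analysis.** A reader might infer that changes will be compared in pg/mL. The unit is given only where absorbance is read off a standard curve, and the objective leaves change undefined. The wording also allows a comparison of day-28 values or of percentage changes. Mann-Whitney on percentage change ranks patients exactly as Mann-Whitney on log change does, and has about 41%, 55% and 76% power at σ = 1.0 for ρ of 0.3, 0.5 and 0.7. This objection stands: the large loss belongs to one permitted reading. Even so, ANCOVA (60%, 68%, 84%) does better than these alternatives, and the ambiguity is itself a reason to specify.

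**The log scale alone is not enough.** A reader might think that testing the change in log value settles the matter. It does not. At σ = 1.0 and ρ = 0.3 it has 44% power, against 55% for plain Mann-Whitney on day-28 values. This also stands, and is why the baseline covariate belongs in the fix.

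**Error inflation.** A reader might infer that leaving the test open materially inflates the false-positive rate. The excess is 6.0−5 = 1.0 to 6.7−5 = 1.7 points, and arises only if both tests are run and the smaller P value is reported. The protocol does not say this will happen. Pairing mean and SD with median and range suggests a choice by distribution, which shows no clear inflation.

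**Every power input is assumed.** True. With mild skew (σ = 0.5) and ρ of 0.5 or 0.7, Mann-Whitney on raw change already has 90–98% power.

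**Conclusion.** The point holds as a conditional one. The plan states neither the scale nor any baseline adjustment for the cytokines. If values are right-skewed with log-SD around 1.0 and the absolute change is tested, about 30 points of power are lost with Mann-Whitney and 38–48 with the t-test, relative to log ANCOVA. If day-28 values are compared by Mann-Whitney, the loss is 6–30 points, depending on the correlation. At log-SD 0.5 it is about 2–22 points on raw change and about 1 point for Mann-Whitney on day-28 values. All of this assumes log-normal values, a true halving, 20 per arm with no dropout, and ρ of 0.3 to 0.7.

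Log ANCOVA had the highest power in every setting tabulated, or was level where power was near 100%, with type I error of about 5%. The documents do not support a claim that the planned comparison must lose much of its power, nor one of serious error inflation. This is a minor point on a secondary endpoint in a self-described pilot, and it leaves the 180-day mortality comparison untouched.

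**What to change.** Add one or two sentences to Section 4, Statistical Analysis:

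- Each of IL-1b and IL-6 is analysed once, on the log scale, by ANCOVA of the log day-28 value on arm and log baseline.
- The result is reported as a ratio of geometric means (FMT to SOC) with its 95% CI.
- Values below the assay limit are set to a fixed, stated value before logs are taken.
- Mann-Whitney is a sensitivity analysis only. An unadjusted change in log value should not be the primary test.

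Day 28 should also be added to the listed analysis times, which at present are baseline and days 7, 30 and 90.

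Cost: no new patients, samples or assays. Results will read as ratios rather than pg/mL differences, and a little power is given up if the values turn out close to symmetric.
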